6.1.3. Safety outcomes

- ★ Overall rate, severity, and relationship of any adverse event per administration and patient.
- ★ Assessment of local tolerability (tissular reactions in the administration site).
- ★ Changes in standard laboratory parameters (serum chemistry and hematology).

7. Statistical Methods

All statistical analyses will be carried out by Inmunotek.

All computation will be performed according to European Guidelines

7.1. General Considerations

Descriptive statistics will be provided for selected demographic, safety, and exacerbations by dose, dose schedule, and time as appropriate. Descriptive statistics on continuous data will include means, medians, standard deviations (and standard errors for post-baseline data), quartiles, and ranges, while categorical data will be summarized using frequency counts and percentages. Graphical summaries of the data may also be presented.

When data are summarized by time, the values recorded against the scheduled time points listed in the protocol will be used. When assessing minimum/maximum increases or decreases over the study, all assessments, including unscheduled assessments will be used. Data listings will include all available data from all enrolled subjects unless specified otherwise.

This analysis does not use significance levels. Exact, two-sided 95% confidence intervals were used for the Histamine equivalent concentration.

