**10.3. Significance Level to be Used**

The significance level for the efficacy assessment will be 0.05 for a type I error ( $\alpha$ ) and 0.2 for a type II error ( $\beta$ ).

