7.1.1. Sample Size and Power

The calculation of the sample size is based on the efficacy measured based on the decrease in the number of episodes of COPD exacerbations during the 12-month treatment period of the trial per subject.

The ratio of subjects to be distributed among the active treatment and placebo groups will be 1:1.

We estimate that subjects from group I (active treatment with the bacterial vaccine) will achieve a 60% decrease in their number of COPD exacerbations compared with a 30% decrease among those of group II (placebo). With an alpha error of 0.05 and a beta error of 0.2, and assuming a dropout rate of 20-25%, the number of subjects to be recruited would be 90 per study group, with an overall total of 180 trial subjects.

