7.1.5. Multiple Comparison

If multiple comparisons are needed, Holm adjustment for multiple comparisons will be used. However, the analysis will try to obviate multiple comparisons except as exploratory analysis.

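### SAP 7.1 disowns the 0.05 significance level set in protocol 10.3 and SAP 7.1.1, and neither document states its sidedness or the Holm family

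*SAP*

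**What the plan says.** The general section of the SAP (7.1) contains two adjacent sentences on inference: "This analysis does not use significance levels" and "Exact, two-sided 95% confidence intervals were used for the Histamine equivalent concentration".

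Other places in the two documents assume the opposite:

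- Protocol 10.3: "The significance level for the efficacy assessment will be 0.05 for a type I error".
- SAP 7.1.1, repeating protocol 10.2, sizes the trial "With an alpha error of 0.05 and a beta error of 0.2".
- SAP 7.1.5: "If multiple comparisons are needed, Holm adjustment for multiple comparisons will be used". It adds that the analysis will try to avoid multiple comparisons except as exploratory work.
- SAP 7.1.9 assigns the primary endpoint a median test or a Mann-Whitney test. SAP 7.4.1 and 7.4.2 add chi-square or Fisher, Cox, Poisson, t and Mood tests.
- SAP 7.4.1 and 7.4.2 plan 95% CIs for relative risks, the hazard ratio, absolute effects and cost-benefit ratios.

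SAP 7.4.2, headed as secondary efficacy analysis, lists exacerbation analyses by time point, analysis set and COPD severity. It does not say which of them belong to a Holm family or which are exploratory.

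**The concern.** The SAP presents itself as describing all planned analyses, with decisions taken before database lock (SAP 2.1). A reader cannot assume that the protocol silently overrides it. SAP section 8, on deviations from the protocol, does not mention dropping the significance level.

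As it stands, the SAP supports two opposite readings. On one, nothing is tested against a threshold and the trial is descriptive. On the other, 0.05 applies, but to an open set of tests, because SAP 7.4.1 lists several methods under the primary analysis, SAP 7.4 runs efficacy on all analysis sets, and the Holm family is not defined. What counts as a positive primary result, and which secondary results may be called significant, could then be settled after the data are seen.

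**Working it through.** **Step 1. Is there a threshold, and what is it?** Protocol 10.3 gives alpha 0.05. SAP 7.1.1 gives alpha 0.05 with beta 0.2, that is, 80% power. The two agree, and only SAP 7.1 conflicts with them. Holm compares ordered p-values with alpha/m, alpha/(m − 1) and so on, so SAP 7.1.5 cannot be carried out under SAP 7.1 as written.

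**Step 2. Does the trial measure the quantity in the CI rule?** No histamine equivalent concentration appears among the outcomes in protocol 5.1 or SAP section 6. The sentence has no object in this trial.

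**Step 3. Can the sidedness be recovered from the sample size?** The inputs, from SAP 7.1.1, are a 60% versus 30% decrease, alpha 0.05, power 80%, dropout 20-25% and 90 per group.

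Read as two proportions, with p̄ = 0.45:

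n = [z_α √(2 p̄(1 − p̄)) + z_β √(p₁(1 − p₁) + p₂(1 − p₂))]² / (p₁ − p₂)²

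- Two-sided: (1.960 × √0.495 + 0.842 × √0.45)² / 0.09 = 42 per group. After dropout: 42/0.80 = 53 to 42/0.75 = 56.
- One-sided: (1.645 × √0.495 + 0.842 × √0.45)² / 0.09 = 33 per group. After dropout: 42 to 44.
- With continuity correction: 49 two-sided (62 to 66 after dropout) and 40 one-sided (50 to 54).

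None of these gives 90.

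Read as a count, the calculation needs a baseline rate b and a dispersion k, and neither document gives them. I assume b = 2 to 4 exacerbations per year and k = 0 to 1.5, with rates 0.4b and 0.7b, two-sided alpha 0.05 and power 80%:

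n = (z_α/2 + z_β)² (1/0.4b + 1/0.7b + 2k) / [ln(0.4/0.7)]²

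This gives 25 (b = 4, k = 0) to 125 (b = 2, k = 1.5) per group, or 32 to 167 after dropout. The planned 90 lies inside that range. The sample size therefore does not reveal the sidedness, and this failure to reproduce 90 does not show that 90 is wrong.

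**Step 4. How many cuts does SAP 7.4.2 list?**

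| Analysis | Horizons × groups | Cuts |
|---|---|---|
| First exacerbation, ITT and PP | 4 × 2 | 8 |
| First exacerbation, moderate and severe | 4 × 2 | 8 |
| Any exacerbation, ITT and PP | 4 × 2 | 8 |
| Number, mild, moderate and severe | 4 × 3 | 12 |
| Number, ITT and PP | 3 × 2 | 6 |
| **Total** | | **42** |

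Splitting the severity groups by ITT and PP as well gives 50 (first exacerbation only) or 62 (both severity rows). In the other direction, two cuts (number at 12 months, ITT and PP) repeat the primary count, and four concern mild COPD, which the entry criteria in SAP 5.2.1 do not admit. Removing both leaves 42 − 2 − 4 = 36.

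**Step 5. What would unadjusted testing at 0.05 do?** If the tests were independent, the chance of at least one false positive is 1 − 0.95^m:

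- m = 36: 84%
- m = 42: 88%
- m = 50: 92%

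If the tests were perfectly correlated it would be 5%. The first Holm step for m = 42 is 0.05/42 = 0.0012.

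**The case against.** The strongest reply is that both sentences in SAP 7.1 are carried-over text. The histamine sentence is in the past tense, and the same section promises summaries by dose and dose schedule although the trial has one regimen against placebo. The SAP says it is based on the protocol, the protocol sets 0.05, and the SAP repeats it. This stands as an account of how the sentences got there, and it makes the intended value easy to recover. It does not remove the contradiction, because the first sentence is a general rule in the governing analysis document.

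Four stronger readings are tempting, and the documents do not support them:

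- A reader might infer that the trial has no decision threshold. Protocol 10.3 and SAP 7.1.1 give one.
- A reader might infer that the stated 80% power is meaningless. SAP 7.1.1 gives alpha and beta together.
- A reader might infer that no confidence intervals are planned for the real endpoints. SAP 7.4.1 and 7.4.2 plan them for the main effect measures.
- A reader might take 88% as the trial's false-positive rate. The horizons are cumulative, ITT and PP overlap, and SAP 7.4.2 says only that these cuts will be studied, without assigning a test to each. If SAP 7.1 were followed literally, nothing would be declared significant and the figure would not arise.

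It is also fair that SAP 7.1.5 leans towards exploratory use of multiple comparisons. That is an intention, though, and SAP 7.4.2 does not apply the label to any of its cuts.

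**Conclusion.** The point holds as a contradiction that must be corrected. The intended alpha is almost certainly 0.05, since both documents give that value. Two pieces are missing: its sidedness, and the family to which Holm would apply.

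The multiplicity exposure is about 42 cuts (36 to 62 depending on how they are counted). Under unadjusted testing at 0.05, the familywise error for 42 would lie between 5% and 88%. The upper figure assumes independence and is an illustration only. The documents do not allow a closer value because they give no correlations. The 42 also leave out hospitalizations, CAT and costs. The contradiction itself does not depend on any of these counts.

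**What to change.** All changes are to SAP wording:

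1. Delete both sentences in SAP 7.1.
2. State alpha 0.05 and its sidedness. Two-sided would match the planned 95% CIs.
3. Attach that alpha to one primary comparison: number of exacerbations over 12 months (the horizon of the sample-size text), in the ITT/FAS set, with one named test in place of the alternatives in SAP 7.1.9 and 7.4.1. Say which ITT definition applies, because protocol 10.7 requires a week 25 assessment and protocol 10.1 and SAP 5.1.2 do not.
4. Choose one of two routes for the secondary outcomes, which is the sponsor's decision. Either list the 12-month outcomes that form the Holm family, or label all secondary analyses exploratory. For scale, if the family were the ten clinical and economic outcomes in SAP 6.1.2, the first Holm step would be 0.05/10 = 0.005.
5. Report the other time-point, PP and severity-group cuts in SAP 7.4.2 as estimates with 95% CIs and no significance claims.

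No new data or patients are needed. The cost is that significance cannot be claimed for those cuts. The change should be dated and made before unblinding. If that has passed, protocol 10.6 already requires the final report to describe deviations from the statistical plan, and this belongs there.

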7.1.1. Sample Size and Power

The calculation of the sample size is based on the efficacy measured based on the decrease in the number of episodes of COPD exacerbations during the 12-month treatment period of the trial per subject.

The ratio of subjects to be distributed among the active treatment and placebo groups will be 1:1.

We estimate that subjects from group I (active treatment with the bacterial vaccine) will achieve a 60% decrease in their number of COPD exacerbations compared with a 30% decrease among those of group II (placebo). With an alpha error of 0.05 and a beta error of 0.2, and assuming a dropout rate of 20-25%, the number of subjects to be recruited would be 90 per study group, with an overall total of 180 trial subjects.

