### **10. STATISTICS**

#### **10.1. Description of the Statistical Methods to be Used, Including the Schedule of any Planned Interim Analysis**

The study analysis will be performed after the database lock. The intention-to-treat (ITT) population will be composed of subjects who took at least one dose of the trial medication. The analysis will be performed on both the ITT and per-protocol populations.

The randomization will be evaluated by comparing the baseline variables (month 0) in both study groups according to the Consolidated Standards of Reporting Trials (CONSORT) due to their clinical relevance. Qualitative variables will be reported together with their frequency distribution, and quantitative variables will be reported together with their mean and standard deviation, or, in case of asymmetry, with their median and interquartile range. If confounding is detected, the effects will be adjusted with the potentially confounding variables using the appropriate model adjustments.

The following variables will be analyzed to determine whether they follow a normal distribution: number of exacerbations, duration of the episodes, need for antibiotic therapy, number of hospital admissions, duration of the hospital admissions, immunological outcomes described in the trial design (page 67), quality of life, and direct costs.

These variables will be described together with their mean and standard deviation, or, in case of asymmetry, with their median and interquartile range. Differences between the means will be analyzed using Student's T test in the case of variables with a normal distribution and Mood's median test in the case of variables without a normal distribution. The absolute effect (difference in estimators) and its precision will be estimated with a 95% confidence interval (CI) in all cases.

The rate of exacerbations per patient and the severity of these exacerbations will be compared using the chi-square test or Fisher's exact test. The relative risks will be estimated together with their 95% CI. The number needed to treat (NNT) or number of events prevented per treatment will be estimated.

The rate of episodes occurred over time will be calculated, and the hazards ratio (HR) will be estimated together with its 95% CI following a Cox proportional-hazards model. The NNT (number of patients that need to be treated to avoid an event) will also be estimated.

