To compare the change in the immunological variables described in the trial design (page 67) at 0, 3, 6, 12, and 18 months, an analysis of covariance will be performed, estimating the mean difference over time in both study groups.

The cost-benefit ratios in the study groups will be estimated together with their 95% CI, and compared using non-parametric tests.

The safety variables will be compared using the chi-square test in the case of qualitative variables or Student's T test in the case of quantitative variables whenever they meet parametric assumptions, or using non-parametric test in the opposite case.

The statistical software that will be used is STATA 11.

---

**10.2. Number of Anticipated Subjects and Rationale. Calculation Method Used for Determining the Sample Size and Data Used for Such Purpose**

The calculation of the sample size is based on the efficacy measured based on the decrease in the number of episodes of COPD exacerbations during the 12-month treatment period of the trial per subject.

The ratio of subjects to be distributed among the active treatment and placebo groups will be 1:1.

We estimate that subjects from group I (active treatment with the bacterial vaccine) will achieve a 60% decrease in their number of COPD exacerbations compared with a 30% decrease among those of group II (placebo). With an alpha error of 0.05 and a beta error of 0.2, and assuming a dropout rate of 20-25%, the number of subjects to be recruited would be 90 per study group, with an overall total of 180 trial subjects.

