5.1.2. Intention to Treat Set or Full Analysis Set (FAS)

All randomized subjects who have taken at least one dose. These subjects will be assigned to the corresponding treatment group.

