7.1.9. Model Assumptions

Primary endpoint analysis will use a median test or a Mann-Whitney test. Secondary endpoints will use relevant tests (Fisher's exact, T test, etc.) and a Poisson regression for exacerbations with baseline characteristics as covariates.

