7.4.1. Primary Efficacy Analysis

The rate of exacerbations per patient and the severity of these exacerbations will be compared using the chi-square test or Fisher's exact test. The relative risks will be estimated together with their 95% CI and median or Mann-Whitney tests. The number needed to treat (NNT) or number of events prevented per treatment will be estimated.

The rate of episodes occurred over time will be calculated, and the hazards ratio (HR) will be estimated together with its 95% CI following a Cox proportional-hazards model. The NNT (number of patients that need to be treated to avoid an event) will also be estimated.

Poisson model with robust estimation of incidence density will be used to include covariates in the model.

Poisson model assumes that the response variable is a count variable (number of exacerbations) and each subject has the same length of observation time. If the observation time for subjects varied, the Poisson model would need to be adjusted to account for the varying length of observation time per subject. In this case a Stata exposure option, *exposure(varname)*, will be used where *varname* corresponds to the length of time an individual was followed to adjust the Poisson regression estimates. Also, Poisson model assumes that the dependent variable is not over-dispersed and does not have an excessive number of zeros (in whose case Negative Binomial and Zero-inflated models would be preferred).

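### The 90 per group for 80% power does not follow from the stated inputs, and the 80% is tied to no single planned test

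*SAP*

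**What the plan says.** SAP 7.1.1 and protocol 10.2 carry the same paragraph. The calculation rests on the "decrease in the number of episodes of COPD exacerbations during the 12-month treatment period of the trial per subject". The inputs are a 60% decrease on vaccine and 30% on placebo, alpha 0.05, beta 0.2, 1:1 allocation and 20-25% dropout. The result is that "the number of subjects to be recruited would be 90 per study group, with an overall total of 180 trial subjects". No baseline rate, standard deviation, dispersion, sidedness, formula or test is given.

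The test for the primary endpoint differs by section:

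- SAP 7.1.9: "Primary endpoint analysis will use a median test or a Mann-Whitney test".
- SAP 7.4.1, the primary efficacy analysis, opens with "The rate of exacerbations per patient and the severity of these exacerbations will be compared using the chi-square test or Fisher's exact test". It then adds relative risks with median or Mann-Whitney tests, a Cox model, and a robust Poisson model with negative binomial or zero-inflated alternatives.
- Protocol 10.1, for a list of variables that includes the number of exacerbations: "Differences between the means will be analyzed using Student's T test in the case of variables with a normal distribution and Mood's median test", the latter for non-normal variables.

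SAP 7.1 also states that the analysis uses no significance levels, although the sample size section sets alpha at 0.05.

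**The concern.** A sample size statement should let a reader recover the number from its inputs and see which analysis the power belongs to. Here neither is possible. The percentages look like two proportions, but on that reading 90 is far more than 80% power needs. The text describes a count per subject, and a count cannot be sized without a rate and a measure of variability.

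What is at stake is how the result will be read. If the primary comparison is null or borderline, readers will lean on the 80%. If several tests of different power can all serve as primary, the figure describes none of them and the choice among them stays open.

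**Working it through.** **Inputs from the documents (SAP 7.1.1, protocol 10.2).** 60% and 30% decrease; alpha 0.05; power 80%; 1:1; dropout 20-25%. Ninety recruited leaves 90 × 0.75 = 67.5 to 90 × 0.80 = 72 evaluable per arm.

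**Assumptions, because the documents give no value.** Two-sided test; baseline rate b of 2 to 4 per year; negative binomial dispersion k of 0 to 1. The entry criteria (SAP 5.2.1) do not fix the rate: they admit three moderate exacerbations in the last year, or two with at least one hospitalised.

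**1. Can 90 be reproduced from the stated inputs alone?** Only the two-proportion reading can be computed without adding an input.

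n = [1.960 × √(2 × 0.45 × 0.55) + 0.842 × √(0.6 × 0.4 + 0.3 × 0.7)]² / 0.30² = 41.97, so 42 per arm.

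Continuity-corrected: (41.97/4) × [1 + √(1 + 4/(41.97 × 0.30))]² = 48.41, so 49.

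Recruited: 42/0.80 = 53 and 42/0.75 = 56; 49/0.80 = 62 and 49/0.75 = 66.

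Unpooled (40) and arcsine (42) versions give much the same. One-sided versions need fewer (33, or 40 corrected). None comes near 90.

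Power on this reading is Φ{[0.30 × √n − 1.960 × √0.495] / √0.45}: 94.6% at 67, 95.4% at 70 and 95.9% at 72 evaluable.

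**2. What would make 90 right for the count?** With equal baseline rates, the on-trial means are m0 = 0.7b and m1 = 0.4b, a rate ratio of 0.40/0.70 = 0.571. For a rate model:

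n = (1.960 + 0.842)² × (1/m0 + 1/m1 + 2k) / [ln 0.571]²

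At b = 3 the means are 2.1 and 1.2, and n = 7.85 × (1.310 + 2k) / 0.313:

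| k (b = 3) | evaluable per arm | recruited per arm |
|---|---|---|
| 0 | 33 | 42-44 |
| 0.5 | 58 | 73-78 |
| 0.75 | 71 | 89-95 |
| 1 | 83 | 104-111 |

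Solving for k at 67.5 to 72 evaluable gives 0.36-0.45 at 2 per year, 0.69-0.78 at 3 and 0.86-0.95 at 4. If the decrease is taken as a mean percentage change, the SD must be 30 × √(n/2)/2.80 = 62 to 64 points. None of these values is in either document.

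**3. Can one 80% serve the listed tests?** Simulated gamma-Poisson counts over 12 months, b = 3, 70 completers per arm, two-sided 0.05; approximate power:

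| k | Mann-Whitney | median test (no continuity correction) | robust Poisson |
|---|---|---|---|
| 0.5 | 81% | 70% | 88% |
| 0.74 | 71% | 58% | 81% |

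The two tests in SAP 7.1.9 differ by 81 − 70 = 11 and 71 − 58 = 13 points on the same data. Ninety recruited fits Mann-Whitney at k of about 0.5, or a rate model at k of about 0.74, but no single k gives 80% for both.

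**4. Range over the assumptions (b = 2-4, k = 0-1).** The partial column takes 22.5% dropout per arm at a uniform time, with exposure used in the Poisson model only.

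| Test | 70 completers | 90, partial follow-up | 90 complete |
|---|---|---|---|
| Robust Poisson | 67 to >99% | 73 to >99% | 77 to >99% |
| Mann-Whitney | 55 to >99% | 59 to >99% | 65 to >99% |
| Median test (uncorrected) | 45-98% | 44-98% | 53 to >99% |

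Under no effect, rejection rates with 70 completers and with 90 on partial follow-up were 3.0-5.3%. The simulations compare on-trial counts and do not use each subject's baseline count.

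**The case against.** The strongest reply is that 90 may simply be conservative. On the proportion reading it is more than enough, and under plausible count inputs it is adequate. That stands: nothing here shows that 90 is too few.

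A reader might go further and infer that the trial is underpowered, or that the tests in SAP 7.1.9 fall short of 80%. The documents do not support that. The shortfall at k = 0.74 arises because that k was solved to give a rate model 80%, so less efficient tests must come out lower. At k = 0.5 Mann-Whitney reaches about 81%, and the documents favour neither value. Nor is a shortfall established for the full analysis set. It keeps "All randomized subjects who have taken at least one dose", SAP 7.4.1 says that with unequal follow-up "the Poisson model would need to be adjusted to account for the varying length of observation time per subject", and protocol 6.3.3 replaces some early withdrawals. Power there depends on dropout timing, which is not stated.

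A reader might also want power figures for the chi-square, Fisher and Cox analyses. SAP 7.4.1 does not define the binary outcome or the event that these would use, so any figure would belong to an endpoint of the reader's own making.

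Finally, recruitment was due to end on 31 March 2018 (protocol 5.5) and the SAP cites 2021 guidance, so the sample size can no longer change. That also stands. It limits the remedy to the choice of test and an honest power statement, both of which still matter before unblinding.

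**Conclusion.** The point holds as one about an unsupported figure. It is neither a proven wrong sum nor evidence of too few subjects. The only calculation possible from the stated inputs gives 53 to 66 recruited per arm, against 90 stated, and about 95% power at the planned evaluable size. This rests on a two-sided test. The count endpoint that the text names cannot be sized without a rate and dispersion that are absent.

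The more consequential part is that the 80% belongs to no identified test. Under the same inputs the two tests named in SAP 7.1.9 differ by about 11 to 13 points, so the figure cannot be true of both. That comparison rests on an assumed 3 per year, k of 0.5 or 0.74, and 70 completers per arm. The sponsor should correct this; it does not put the trial's size in question.

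**What to change.** Keep the planned 180. Then:

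1. Before unblinding, name one primary test for the 12-month number of exacerbations and make the others supportive. The robust Poisson model with an exposure term, or its negative binomial alternative, is already in SAP 7.4.1. Robust Poisson was the most powerful of the tests simulated.
2. In SAP 7.1.1, give the planning method, sidedness, baseline rate and variability if they can be retrieved. If not, say that the basis is undocumented. Replace the 80% with a power range for the chosen test, labelled as a restatement, over assumed rates of 2-4 per year and dispersion of 0-1. Give it for 67-72 completers and for 90 per arm.
3. Reconcile this with the SAP 7.1 statement that no significance levels are used.
4. Leave protocol 10.2 as written and declare the change under protocol 10.6.

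The cost is one SAP paragraph, a decision on the primary test and one declared deviation, with no added patients. The downside is that the stated power may look less favourable and will rest on assumed inputs.
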